## 6.2 Participant disposition

For the Screened Set, the number and percentage of participants screened, randomized/assigned, who are vaccinated with each IMP dose, including the number of participants who are eligible for Dose 2 (Cohorts 1 to 4 only), the number of participants who received Dose 2 and non-vaccinated participants will be summarized. The number of participants that discontinued treatment together with the primary reason for treatment discontinuation as well as participants that discontinued the trial together with the primary reason for trial discontinuation will be summarized. Also, the participants who discontinued trial after Dose 1 and before Dose 2, and after Dose 2 will be summarized.

CCI

Participant-wise listings for disposition with randomization scheme, IMP doses received, trial completion status, and withdrawal reason will be presented.

The number and percentage of participants in each analysis set will be summarized with Randomized/Assigned Set. In addition, the number and percentage of participants excluded from each analysis set will be presented by treatment group along with the reasons for exclusion.

Participants excluded from analysis sets will also be listed.

The number and percentage of participants in the Safety Set with Key PDs will be summarized by PD category and sub-category. PDs will be presented in participant-wise listings as well.

## 6.3 Baseline characteristics

### 6.3.1 Demographics and baseline characteristics

Demographic and baseline characteristics data will be summarized on the Randomized /Assigned Set, Safety Set, Dose 2 Safety Set, and Immunogenicity Per Protocol Set.

Age at screening (years) will be summarized as continuous data. Sex (male or female), childbearing potential (yes or no; percentage is based on the number of female participants), race (Black or African American, American Indian or Alaska Native, Asian, Native Hawaiian or Other Pacific Islander, White, other, Multiple, Not reportable / Unknown) and Ethnicity (Hispanic or Latino, Not Hispanic or Latino, Not reportable / Unknown), N-binding antibody status at screening (positive or negative), and N-binding status (positive, negative, or indeterminable ) at pre-Dose 1, will be summarized as categorical data.

Height (cm), weight (kg), and BMI ( $\text{kg}/\text{m}^2$ ) at screening will be summarized descriptively. BMI category Underweight (below 18.5), Normal weight (18.5 - < 25.0), Overweight (25.0 - < 30.0), and Obese (30.0 and above) will be summarized with frequency counts and percentages.

### **6.3.2 Prior and concomitant medication/vaccination/procedures/non-drug therapy**

Prior and concomitant medications will be defined using medication start and stop dates recorded relative to first dose of IMP administration.

If the medication/procedure started and stopped before the date of the first dose of trial IMP, the medication/procedure will be assigned as being prior to trial IMP. Otherwise, the medication/procedure will be assigned as being concomitant with trial IMP.

Medications will be coded using the World Health Organization Drug Dictionary (WHODrug) drug codes of version B3 March 2022 or later resulting in Anatomical Therapeutic Chemical (ATC) codes indicating therapeutic classification.

The number and percentage of participants who had prior medications and concomitant medications/vaccinations will be summarized by ATC classification level 4 and preferred name by treatment group for participants in the Safety Set. The summary will be sorted by ATC alphabetically and, within each ATC, the preferred names will be sorted by descending frequency. If ATC level 4 is not available, the highest level available will be presented, e.g., level 3, 2 or 1.

Concomitant medications administered due to local reactions and systemic events after each IMP dose administration will also be summarized.

Concomitant procedures and non-drug therapies will be coded using the most recent version of the Medical Dictionary for Regulatory Activities (MedDRA®) coding system. Concomitant procedures and non-drug therapies will be listed only.

Prior COVID-19 vaccination history will also be presented. The number of prior COVID-19 vaccinations and time from the last vaccination to Dose 1 (days) will be summarized based on Safety Set and Immunogenicity Per Protocol Set, and listed.

### **6.3.3 Medical history and prior SARS-CoV-2 infection**

Medical history and prior SARS-CoV-2 infection data will be coded using the most recent version of the MedDRA® coding system. The number and percentage of participants with each medical history and surgery will be summarized by System Organ Class (SOC) and Preferred Term (PT) by treatment group, for participants in the Safety Set. The summary will be sorted by SOC alphabetically and, within each PT, the PT will be sorted by descending frequency.

Prior SARS-CoV-2 infection data will be summarized including the type of test, time from the last infection to Dose 1 (days), and infection with SARS-CoV-2 Omicron variant confirmed (yes, no or unknown) with number and percentage of participants based on Safety Set and Immunogenicity Per Protocol Set.

A listing of medical history, prior SARS-CoV-2 infection and surgery data will be provided.

## 6.4 Efficacy analysis

Efficacy endpoints are not defined in the protocol and efficacy analysis will not be conducted.

## 6.5 Safety analysis

The primary endpoints are safety endpoints and are described in the below sections and in Section 1.1.

### 6.5.1 Primary endpoint safety analysis

#### 6.5.1.1 Local reactions

The local reactions assessed and reported in the e-diary are pain, erythema/redness and induration/swelling within seven days after each trial IMP dose administration.

Solicited local and systemic events that are recorded in the participant e-diaries should not be reported as AEs unless they meet criteria for a serious adverse event (SAE) or start at Days 1 to 7 and continue past Day 7.

Solicited local reactions will be categorized as mild, moderate, severe, potentially life-threatening and graded from 1 to 4, during the analysis as described in [Table 5](#). The categories and grades are based on the US Food and Drug Administration (FDA) Guidance for Industry: [“Toxicity Grading Scale for Healthy Adult and Adolescent Volunteers Enrolled in Preventive Vaccine Clinical Trials”](#).

**Table 5: Local reaction grading scale**

	Mild (Grade 1)	Moderate (Grade 2)	Severe (Grade 3)	Potentially life-threatening (Grade 4)c
Pain	Does not interfere with activity	Interferes with activity	Prevents daily activity	Requires attendance at an emergency room or hospitalization for severe pain
Erythema / rednessa	2.5 cm to 5.0 cm (0.98 in to 1.96 in)	>5.1 cm to 10.0 cm (>1.96 in to 3.94 in)	>10 cm (>3.94 in)	Necrosis or exfoliative dermatitis
Induration / swellingb	2.5 cm to 5.0 cm	>5.1 cm to 10.0 cm	>10 cm	Necrosis

Source: Based on the US FDA guidance for industry [“Toxicity Grading Scale for Healthy Adult and Adolescent Volunteers Enrolled in Preventive Vaccine Clinical Trials”](#).

- a. In addition to grading the measured local reaction at the greatest single diameter, the measurement should be recorded as a continuous variable.
- b. Induration/swelling should be evaluated and graded using actual measurement.
- c. Investigator or medically qualified person confirmation is required for all reactogenicity graded as Grade 4.

For participants recording at least one local reaction within seven days after each trial IMP dose administration, in the case of different value between participant reported and investigator confirmed results, investigator confirmed result will be included in the analysis:

- The maximum severity grade is equal to the highest graded local reaction within the recording period.
- Duration will be calculated in days as the difference from the start of the first reported event to the resolution of the last reported event, inclusive. The resolution date for events lasting longer than 7 days will be recorded in the participant's adverse event case report form. If the resolution date is partial or missing, the duration will be considered unknown.
- Onset day, defined as the first day of reporting any severity, will be derived for each recorded local reaction. If a participant report changes in severity of the local reaction, only the first day of reporting that specific local reaction will be counted.

The number and percentage of participants reporting local reactions up to seven days after each IMP dose administration will be summarized by maximum severity and cumulatively across severity levels. This summary will include categories "Any", "Grade 1", "Grade 2", "Grade 3", and "Grade 4". The associated 2-sided Clopper-Pearson 95% CIs will also be displayed.

The Safety Set and Dose 2 Safety Set will be used for post-Dose 1 and post-Dose 2 local reaction summaries respectively. Participants without any reactogenicity data up to seven days after each IMP dose administration will be excluded from the local reaction analysis. Missing values will not be imputed.

In addition, local reactions will also be summarized by:

- Duration (days) of each local reaction after each IMP dose.
- Onset day of each local reaction after each IMP dose.

Bar charts with the proportions of participants for each local reaction up to seven days after each IMP dose administration will be plotted. The bars will be divided into severity categories to highlight the proportions of participants by maximum severity. In addition, a listing of participants in the Safety Set with reported local reactions will be provided.

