8.2.5 Subject e-diaries for assessment of reactogenicity (local and systemic reactions)

Subject e-diaries will be issued to trial subjects, trained, and collected by trial site personnel at the visits given in the SoAs (Section 1.3 and Section 13.5).

Subjects will be asked to:

- Report reactogenicity (incl. oral body temperature) daily for 7 d after each IMP dose using an e-diary.
- Record the worst grade for each symptom approximately the same time every evening.
- Contact the site if they experience any severe or potentially life-threatening reactogenicity events.
- Report the use of antipyretic/analgesic medication to treat symptoms associated with IMP administration for 7 d after each IMP dose using an e-diary.

If a local and/or systemic reaction persists beyond the end of the reactogenicity e-diary period following vaccination, the trial subject will be requested to report that information to the investigator. Solicited local and systemic events that are recorded in the subject e-diaries should not be reported as AEs unless they meet criteria for an SAE or starts at Days 1 to 7 and continues past Day 7.

Note: in case an e-diary entry was missed, or the e-diary did not work, the site personnel will ask if any reactogenicity event occurred. The site will record reported events that were not entered in the e-diary on the AE page of the CRF.

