- Record the worst grade for each symptom in the e-diary at approximately the same time every evening on the day of IMP injection and then every day in the evening for a total of seven consecutive days.
- Measure their oral body temperature using the provided device and record their body temperature in the e-diary every day including the day of IMP injection.
- To assess any solicited local reactions at the injection site as described in Section 8.2.5.1 and solicited systemic reactions as described in Section 8.2.5.2.
- To contact the site immediately in case of severe or potentially life-threatening reactogenicity events.

- To report if an e-diary entry was missed or if the e-diary did not work; if any such events occurred, the site will record them (e.g.) on the AE page of the CRF.

Investigators will review subject e-diary data daily as indicated in the SoAs (Section 1.3 and Section 13.5).

Only an investigator or medically qualified person is able to confirm a trial subject's fever as $>40.0^{\circ}\text{C}/>104.0^{\circ}\text{F}$ (a potentially life-threatening Grade 4 event) for recording in the electronic data capture (EDC) system.

If a trial subject experiences confirmed Grade 4 reactogenicity, the investigator must immediately notify the sponsor and, if it is determined to be related to the administration of IMP, further IMP administration (if applicable) will be discontinued in that trial subject (see Section 7.1).

If a trial subject experiences a potential Grade 4 reactogenicity, and the grading is confirmed by the investigator or some other medically qualified person, the confirmed Grade 4 reactogenicity will be recorded by the investigator as an SAE.

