Systemic events reported up to seven days post-Dose 1 and post-Dose 2 will be summarized in the same manner as local reactions (see Section [6.5.1.1](#) using the Safety Set and Dose 2 Safety Set. Participants without any reactogenicity data up to 7 days after each IMP dose administration will be excluded from the systemic events analysis. In addition, a listing of participants in the Safety Set with reported systemic events will be provided.

If data regarding local /systemic reactogenicity events were not entered into the e-diary tool as planned, and instead were recorded on the AE CRF page, SDTM data reconstruction will be implemented to align with the FDA guidance outlined in "[Submitting Study Datasets for Vaccines to the Office of Vaccines Research and Review](#)".

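### Any reaction duration above 7 days needs a complete AE CRF end date; without one the SAP sets it to unknown with no minimum, so mean and sometimes maximum duration are likely understated

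*SAP*

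**What the plan says.** SAP 6.5.1.1 defines duration as the inclusive number of days from the first reported day of a reaction to its resolution. For prolonged reactions it states: "The resolution date for events lasting longer than 7 days will be recorded in the participant's adverse event case report form". The next sentence is the rule at issue: "If the resolution date is partial or missing, the duration will be considered unknown". The planned output is "Duration (days) of each local reaction after each IMP dose". SAP 6.5.1.2 handles systemic events in a similar way and names duration among the shared derivations.

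The SAP gives no fallback. Section 6.5.1.1 rules out imputation, and the date rules for AEs in 6.1.4 serve only to assign the post-dose flag. Continuous variables are summarised by n, mean, SD, median, minimum and maximum (SAP 6.1.1). The SAP does not say whether unknown durations will be counted in the table.

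Several kinds of reaction reach the AE page of the CRF:
- Diary reactions that "start at Days 1 to 7 and continue past Day 7", or that meet SAE criteria (SAP 6.5.1.1).
- Reactions missed in the diary, whatever their length. Protocol 8.2.5 says: "The site will record reported events that were not entered in the e-diary on the AE page of the CRF". SAP 6.5.1.2 likewise provides for reactions that "were not entered into the e-diary tool as planned, and instead were recorded on the AE CRF page".
- Confirmed Grade 4 reactions, also whatever their length: "the confirmed Grade 4 reactogenicity will be recorded by the investigator as an SAE" (Protocol 8.2.6).

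**The concern.** The diary runs from Day 1 to Day 7, so a duration taken from it cannot exceed 7 days. Every longer duration needs a complete CRF end date, while most short ones do not. An incomplete date is therefore more likely to cost the table a long duration than a short one.

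An unresolved reaction has no resolution date, so the rule always makes its duration unknown. The protocol foresees such cases: follow-up may end at stabilisation, loss to follow-up or withdrawal of consent, and a final status may be unavailable (8.3.3). The AE outcome categories include not resolved and unknown (10.4.3).

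The rule also discards information already held. A reaction still present on Day 8 has a known minimum length, and a partial date usually gives one too. At stake is whether the duration tables of a dose-escalation trial show prolonged reactions at their proper weight.

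**Working it through.** The documents give no figure for duration, for the share of reactions running past Day 7, or for missing end dates. There is nothing to reproduce, and what follows is an illustration on stated assumptions.

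**Inputs**
- S = 2 d, the length of an ordinary reaction. This is anchored on Protocol 12.1, which describes resolution of BNT162b2 reactions in 1 to 3 days.
- f = 2% to 10%, the share of reactions running past Day 7 (assumed).
- L = 8 to 14 d, the length of those reactions (assumed).
- m = 25% to 100%, the share of those without a complete end date (assumed).

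**Known minimum.** A reaction with onset on Day k that is still present on Day 8 has lasted at least 8 − k + 1 = 9 − k days. That is 8 days for onset on Day 1 and 2 days for onset on Day 7.

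**Formulas**
- True mean = (1 − f)S + fL.
- Mean with unknown durations left out = [(1 − f)S + f(1 − m)L] / (1 − fm).
- Mean with undated reactions counted at their minimum of 8 d (onset Day 1) = (1 − f)S + f(1 − m)L + 8fm.

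| f | L (d) | m | True mean | SAP rule | Difference | With 8 d minimum |
|---|---|---|---|---|---|---|
| 2% | 8 | 25% | 2.12 | 2.09 | −1% | 2.12 |
| 5% | 10 | 50% | 2.40 | 2.21 | −8% | 2.35 |
| 10% | 14 | 100% | 3.20 | 2.00 | −38% | 2.60 |

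The middle row in full:
- True mean: 0.95 × 2 + 0.05 × 10 = 2.40 d.
- SAP rule: (1.90 + 0.25) / 0.975 = 2.21 d.
- With the minimum: 1.90 + 0.25 + 0.20 = 2.35 d.

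The first and last rows are the extremes of the assumed range. Throughout that range the minimum-duration mean lies between the SAP-rule mean and the true mean, and equals the true mean when L = 8.

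**Median.** At least 90% of reactions last 2 d in every scenario, so the median is 2 d with or without the undated reactions.

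**Maximum.** It changes only if the longest reaction is itself undated. If 80% of 45 vaccinees have a given reaction (36, assumed) and f = 5%, the expected number past Day 7 is 36 × 0.05 = 1.8. The chance of at least one is 1 − 0.95^36 = 84%. One or two undated cases could then decide the reported maximum.

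**Limits on the direction**
- A reaction that passes Day 7 need not be long. With onset on Day 7 and end on Day 8 it lasts 2 d, and losing it leaves the mean of 2 d unchanged.
- Short reactions entered on the CRF can also lack dates. Let s be the undated share of short reactions. The reported mean is then [(1 − f)(1 − s)S + f(1 − m)L] / [(1 − f)(1 − s) + f(1 − m)]. With f = 5%, L = 10 d and m = 25% (true mean 2.40 d), it is 2.30 d at s = 0, 2.40 d at s = 25% and 2.59 d at s = 50%. The bias cancels when s = m and reverses above that.

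**The case against.** The strongest reply is that the protocol works to prevent the gap. AE end dates must be documented in the CRF (10.4.3), AEs are followed to resolution or stabilisation (8.3.3), and subjects are asked to report reactions that outlast the diary (8.2.5). These provisions should keep the undated share small. They do not cover a reaction that is unresolved at last contact.

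Prolonged reactions are also not hidden. They are reported as AEs and appear in the AE listings, and a reaction of unknown duration still counts in the incidence and severity tables. Since n is shown with continuous summaries, a careful reader could notice a shortfall. All of this stands, and it limits the point to the duration summary.

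A reader might infer more than the documents support:
- That past-Day-7 reactions are the only ones needing a CRF end date. Missed diary entries and SAEs, including confirmed Grade 4 reactions, are dated there too.
- That the longest reactions as a class drop out. Only those without a complete date are affected, and their share is not given. Even their omission from the summary is an inference, because the SAP says only that the duration is unknown.
- That a primary endpoint is biased. The primary estimands are frequencies of reactions up to 7 days. Protocol 9.4.2 lists any reaction and maximum severity without mentioning duration, and the SAP adds duration as a further descriptive summary.

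**Conclusion.** The point holds for the descriptive duration summaries of local and systemic reactions. A duration above 7 days enters only with a complete CRF end date, and otherwise the plan keeps no minimum or censored value. Diary-dated short reactions keep theirs, so the mean is likely understated, and sometimes the maximum.

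The direction is likely, not certain. It assumes that unknown durations are left out of the statistics and that end dates are missing more often for long reactions than for short ones. The second assumption is reasonable while the diary is the main source for short reactions.

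The size cannot be derived from the documents. The range of 1% to 38% of the mean rests wholly on the assumed f, L and m, and its upper end requires every past-Day-7 reaction to be undated. The median, incidence, severity tables and primary estimands are essentially unaffected. The trial tests no hypothesis, so no test or sample size changes. This is a desirable improvement to reporting and does not threaten the trial's conclusions.

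**What to change.** In SAP 6.5.1.1, with the same rule carried to 6.5.1.2:
- For each reaction, dose and treatment group, report the number and percentage lasting more than 7 days or unresolved, and the number with unknown duration.
- Treat an incompletely dated reaction as right-censored at the last date it is known to have been ongoing, so that it contributes a minimum duration. Where a partial end date allows, use the earliest date it permits if that is later. Mark any mean or maximum that includes such values as a lower bound.
- Align the two descriptions of what the CRF end date covers. Reactions that continue past Day 7 and reactions that last longer than 7 days are different sets when onset is late.

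A Kaplan-Meier median alone would not be enough: in the illustration it stays at 2 d and shows nothing of the prolonged reactions. The cost is one more derivation rule and a few extra table rows, using data already collected.

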9.4.2 Primary safety endpoints

The safety endpoints are defined in Sections [3](#) and [13.6](#). All safety analyses will be based on the Safety Set.

All AEs will be coded using the most recent version of Medical Dictionary for Regulatory Activities [MedDRA] coding system to get a system organ class and PT for each AE.

Reactogenicity

Solicited local reactions and systemic events (from the subject e-diary or the AE CRF) will be summarized. In general, solicited reactions will be analyzed for each IMP administration, i.e.:

- Up to 7 d after each IMP injection

For each IMP administration, the number and percentage of subjects reporting at least one local reaction or systemic reaction (i.e., solicited data collected using subject e-diaries or the AE CRF) will be summarized for each of the following types:

- Any local reactions or systemic events
- Local reactions or systemic events by maximum severity

Adverse events

All AEs recorded by the investigator are unsolicited events. The number and percentage of subjects reporting at least one AE from Dose 1 will be summarized by PT nested within system organ class for each of the following AE types (for subjects with at least one AE occurring up to 28 d after each IMP administration, and for subjects in Cohorts 1 to 4 with at least one SAE occurring up to 6 months after each IMP administration and for subjects in Cohort 5 with at least one SAE occurring up to 3 months after last IMP administration):

- Any AE
- Grade of AE
- Related AE
- Related Grade ≥ 3 AE
- Any SAE
- Related SAE
- Any AESI
- Related AESI

Moreover, the number and percentage of subjects with any AE will be summarized by worst grade by PT nested within system organ class.

Additional safety analyses may be described in the SAP.

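### For participants with no e-diary entry after a dose, the plan lets the reaction itself decide whether they enter the solicited-reaction denominator

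*SAP*

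**What the plan says.** Four pieces of text bear on this.

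- **Exclusion rule.** SAP 6.5.1.1: "Participants without any reactogenicity data up to seven days after each IMP dose administration will be excluded from the local reaction analysis". SAP 6.5.1.2 repeats it: "Participants without any reactogenicity data up to 7 days after each IMP dose administration will be excluded from the systemic events analysis". Missing values are not imputed.
- **Fallback when the e-diary is missed or fails.** Under Protocol 8.2.5, "the site personnel will ask if any reactogenicity event occurred". What is then written down is limited to positive answers: "The site will record reported events that were not entered in the e-diary on the AE page of the CRF". Protocol 8.2.6 is similar.
- **Use of AE-page reactions.** Protocol 9.4.2: "Solicited local reactions and systemic events (from the subject e-diary or the AE CRF) will be summarized". Its percentages are based on "solicited data collected using subject e-diaries or the AE CRF". For reactions recorded on the AE page instead of the e-diary, SAP 6.5.1.2 says that "SDTM data reconstruction will be implemented".
- **Target population.** The estimand in SAP 1.1 is the frequency among dosed participants.

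The SAP does not define the term reactogenicity data. The version 8.0 change summary in the protocol does apply the term to AE entries in the CRF. SAP 6.5.2.7 will report e-diary non-transmission by treatment group after each dose.

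**The concern.** Take two participants who transmit no e-diary entry after a dose. The site asks both. One reports a reaction; it goes on the AE page, is rebuilt into the reactogenicity data, and puts that person in numerator and denominator. The other reports none; no text describes a record of that answer, so this person has no reactogenicity data and is excluded. Membership of the denominator then depends on the outcome being measured.

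Solicited local and systemic reactions are primary endpoints and are shown side by side by dose level, age group and dose number. E-diary completion may differ between those columns, not least because Dose 2 is open-label, and the distortion would then differ too. The case is foreseen: Protocol 10.4.3 provides for reactions missing from the e-diary for technical or compliance reasons.

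**Working it through.** **Plan figures.** The documents give no expected solicited-reaction rate and no expected e-diary non-completion. The only design figure is SAP Table 3, the probability of at least one AE. It reproduces (2% rate, N=90: 1 − 0.98^90 = 0.838, printed as 0.84), but this point does not depend on it.

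**Assumed inputs.**
- m: share of dosed participants with no e-diary entry at all after the dose.
- r: true rate of any solicited reaction (p_any below).
- s: probability that the site captures a reaction on the AE page when there is no e-diary.

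**Any reaction, missingness unrelated to reacting.** Reported rate = [r(1 − m) + r·m·s] / [(1 − m) + r·m·s]. With s = 1 this is r / [1 − m(1 − r)].

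| m | r = 30% | r = 60% | r = 80% | largest shift over all r |
|---|---|---|---|---|
| 5% | 31.1% | 61.2% | 80.8% | about 1.3 points |
| 10% | 32.3% | 62.5% | 81.6% | about 2.6 points |
| 20% | 34.9% | 65.2% | 83.3% | about 5.6 points |

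The largest shift falls near r = 50%; for example, at m = 5%, 0.50 / (1 − 0.05 × 0.50) = 51.3%. At s = 0.5 the shift is about half; at s = 0 it is zero.

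**A specific reaction with rate pj.** Re-entry depends on having any reaction, so the rate is pj / [1 − m(1 − p_any)]. With p_any between 60% and 80%:
- pj = 10%, m = 20%: 0.10/0.92 = 10.9% down to 0.10/0.96 = 10.4%.
- pj = 10%, m = 10%: 0.10/0.96 = 10.4% down to 0.10/0.98 = 10.2%.
- pj = 5%, m = 20%: 5.4% down to 5.2%.

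**Between columns.** With a true rate of 60% in both, s = 1, and m = 5% in one and 20% in the other, the reported rates are 61.2% and 65.2%, a spurious gap of 4.0 points.

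**When the direction reverses.** Let m = 10%, with 50% reacting among e-diary users and 90% among the rest. The true rate is 0.9 × 0.50 + 0.1 × 0.90 = 54.0%.
- s = 0.2: (0.45 + 0.018)/(0.90 + 0.018) = 51.0%, 3.0 points too low.
- s = 0.5: (0.45 + 0.045)/(0.90 + 0.045) = 52.4%, 1.6 points too low.
- s = 1: 0.54/0.99 = 54.5%, slightly too high.

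**Worked case, N = 45.** Suppose 24 of 40 e-diary users react; of 5 without an e-diary, 3 react and 2 do not. Clopper-Pearson 95% intervals:
- Outcome-dependent denominator: 27/43 = 62.8% (46.7 to 77.0).
- All 45 kept: 27/45 = 60.0% (44.3 to 74.3).
- E-diary users only: 24/40 = 60.0% (43.3 to 75.1).

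**The case against.** A reader might infer that the primary rates are certain to be biased upward. The documents do not support that, for three reasons.

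1. *The mechanism is inferred.* Reactogenicity data is undefined. The CRF is not available, and the SAP does not say whether the reconstruction creates negative records. Protocol 8 requires missed activities to be documented, which might leave a trace. The schedules also include an investigator assessment for up to 1 hour after each dose; if that counts, those assessed stay in and the problem disappears. This stands as a reason to word the point conditionally. It does not remove it: if one of these readings is intended, the SAP needs to say so.
2. *The direction is not fixed.* An upward shift needs complete site capture, or missingness unrelated to reacting with some capture. Partial e-diaries stay in the denominator, and an unrecorded reaction on a missed day lowers the rate. This stands.
3. *Low-rate reactions move little.* Applying the any-reaction formula to a specific 10% reaction at m = 20% gives 0.10/0.82 = 12.2%. That is wrong unless only 10% of participants have any reaction. This stands.

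The consequences are also limited. No hypothesis is tested, no formal dose comparison is planned, and the pausing rule with a 20% threshold (Protocol 7.1.1) concerns unsolicited AEs. The non-transmission table will show readers how much is exposed. These limit the importance, but that table cannot tell a reader how many non-reactors were dropped.

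Finally, restricting the main rate to e-diary users would remove AE-page reactions from a primary safety endpoint, against Protocol 9.4.2. That objection is sound, and the fix respects it.

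**Conclusion.** The point holds in conditional form. Read together, Protocol 8.2.5 and 9.4.2 and SAP 6.5.1.1 and 6.5.1.2 leave a denominator that depends on the outcome for participants with no e-diary entry at all after a dose, and no text closes the gap. It usually pushes rates up and can push them down where sites under-capture reactions in people who react more.

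The sizes in the working rest on assumed missing shares and full capture. At 5% missing, the shift of at most about 1.3 points is small beside an interval of roughly ±15 points at N = 45. At 20% it would be noticeable and could differ between columns. This is more than missing detail, because it touches the denominator of a primary endpoint and departs from the dosed-participant estimand, and it is cheap to repair.

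**What to change.** In SAP 6.5.1.1 and 6.5.1.2:

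- Define the denominator without reference to the outcome: dosed participants with at least one e-diary entry in the 7-day period, or a documented site inquiry after a missed or failed e-diary. Count a negative answer as no reaction.
- Keep AE-page reactions in the main rate, as Protocol 9.4.2 requires.
- Add one sensitivity table for each dose: (a) all dosed participants in the Safety Set or Dose 2 Safety Set, with no record counted as no reaction; (b) only participants with at least one e-diary entry.

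The cost is a few sentences and one extra table. Version (a) may slightly understate rates if sites missed reactions. If inquiries turn out to be documented only where a reaction was reported, the asymmetry stays in the main rate, and (a) and (b) show how much it matters.
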